11.4 Summaries by visit

Visit based safety and PD assessments are generally summarized according to the nominal visit. Except for Visit 18 (EOT/Week 156) in subjects prematurely discontinuing study treatment, Visit 19 (FU7d, Day 7 follow-up assessment for lymphocyte subset only), and Visit 20 (FU, Day 30 follow-up assessment). Those are derived following the rules below:

- Premature EOT visits are re-assigned following the visit windowing described in Section 11.3
- Day-7 follow-up assessment: Any assessment within EOT date + 6 days and EOT date + 15 days. If multiple assessments fall into that period, the one corresponding to the regular FU7d visit (Visit 19) is selected, if none of the multiple assessments corresponds to that visit, the one closest to EOT date + 7 days is selected, if there are two closest assessments, the later one is selected.
- Day-30 follow-up assessment: Any assessment within EOT date + 16 days and EOT date + 37 days. If multiple assessments fall into that period, the one corresponding to the regular FU visit (Visit 20) is selected, if none of the multiple assessments corresponds to that visit, the one closest to EOT date + 30 days is selected, if there are two closest assessments, the later one is selected.

In addition, the ‘Last on-treatment’ assessment is flagged. This is defined to be the latest assessment prior to or on EOT date + 1 day (last on treatment may come from a scheduled or an unscheduled visit).

Summaries by visit are presented by Baseline (derived), and further scheduled nominal visits up to Week 156 (irrespectively if conducted during PTOp or not), Last on-treatment, and derived Follow-up visits (FU7d, FU). Generally, by visit tables are tabulating the baseline and nominal and derived visits as follows:

- Baseline (Note: This is not a nominal visit but the derived baseline; see Section 5.5.1)
- Visit 4 - Week 2

- Visit 5 - Week 4
- Visit 6 - Week 12
- Visit 7 - Week 24
- Visit 8 - Week 36
- Visit 9 - Week 48
- Visit 10 - Week 60
- Visit 11 - Week 72
- Visit 12 - Week 84
- Visit 13 - Week 96
- Visit 14 - Week 108
- Visit 15 - Week 120
- Visit 16 - Week 132
- Visit 17 - Week 144
- Visit 18 - Week 156
- Last on-treatment (derived; see Section 5.5.1)
- Day-7 follow-up (derived) (lymphocyte subset only)
- Day-30 follow-up (derived)

Premature EOT visits are mapped to and summarized within a scheduled visit following the window approach described in Section 11.3; they will not be summarized as “Visit 18 - Week 156” unless they are mapped to this visit as per approach described in Section 11.3.

As per protocol, total lymphocyte counts will be assessed every 4 weeks up to Week 24 (i.e., there are 3 protocol mandated between-visit assessments for those tests at Week 8, Week 16, and Week 20 when no regular visit is scheduled).

These assessments are considered scheduled and are included in corresponding by-visit tabulations labeled as follows:

- Additional Visit - Week 8
- Additional Visit - Week 16
- Additional Visit - Week 20

Visit-based efficacy are summarized according to the nominal visit up to EOS, irrespective if conducted during PTOP or not:

- Baseline (Derived)
- Visit 4 - Week 2
- Visit 6 - Week 12
- Visit 7 - Week 24
- Visit 9 - Week 48
- Visit 11 - Week 72
- Visit 13 - Week 96

- Visit 15 - Week 120
- Visit 17 - Week 144
- Visit 18 - Week 156

Premature EOT visits are mapped to and summarized within a scheduled visit following the window approach described in Section 11.3; they will not be summarized as “Visit 18 - Week 156” unless they are mapped to this visit as per approach described in Section 11.3.

EOS visit is defined for efficacy endpoints and JCV:

- For subjects who complete the treatment period, and for subjects who prematurely discontinue study treatment and do not enter the PTOp, the EOS visit corresponds to the 30 day follow-up visit (FU) for efficacy endpoints, and for the last available visit for JCV.
- For subjects who prematurely discontinue study treatment and enter the PTOp period, the EOS visit corresponds to the last visit of the PTOp.

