AE = adverse event; DBP= diastolic blood pressure; DMF = dimethyl fumarate; eCRF = electronic case report form; eC-SSRS = electronic self-rated version of the Columbia-Suicide Severity Rating Scale; ECG = electrocardiogram; EDSS = expanded disability status scale; EOT = end-of-treatment; FU7d = FU visit approximately 7 days after the last dose of study drug; FS = functional system; FSIQ-RMS = fatigue symptoms and impacts questionnaire – relapsing multiple sclerosis; FU = follow-up; JCV = John Cunningham Virus; MRI = magnetic resonance imaging; MS = multiple sclerosis; MSFC = multiple sclerosis functional composite; OCT = optical coherence tomography; PK = pharmacokinetics, SAE = serious adverse event; SBP = systolic blood pressure; SDMT = symbol digit modalities test; SF-36v2 = 36-Item Short Form Health Survey Version 2; SmPC = Summary of Product Characteristics; USPI = United States Prescribing Information; WPAI-MS = work productivity and activity impairment in MS.

Table 3 Visit and assessment schedule (Part 2)

Periods	Name	TREATMENT PERIOD		FOLLOW-UP		UNSCHEDULED			
	Duration	Up to 60 weeks after randomization of the last subject		30 Days					
Visits	Number	9, 13, 17	18	19	20	I1, I2, ...		R1, R2, ...	U1, U2, ...
	Name	W48, W96, W144	EOT	FU7d (16)	FU (17)	Re-initiation		Relapse	Unscheduled (15)
	Time	Week 48, 96, 144	Up to Week 156 or earlier in case of premature discontinuation	Last study treatment intake + 7 days	Last study treatment intake + 30 days	Day 1 of re-initiation	Day 15 after re-initiation	Any day between Day 1 and EOS	
	Visit window	± 7 days	+ 7 days	± 2 days	+ 7 days	NA	± 1 day	+ 7 days	NA
EDSS/FS*	X	X			X			X	X
Relapse* (1)		X (1) ←						X	
MSFC, SDMT*	X	X							
FSIQ-RMS** (2)	X	X			X			X	X
SF-36v2**	X	X						X	
Health care resource utilization* (3)	X	X						X	
WPAI:MS**	X	X							
Chest X-ray* (4)		X							
eC-SSRS**	X	X							
MRI**	X	X							X
Concomitant medications*	X	X			X			X	X
Physical examination*	X	X						X	X
Body temperature*	X	X			X	X	X	X	X
Pulse rate*								X	X (18)
Dermatological examination* (5)	X	X							X
Body weight*	X	X							X
Systolic/diastolic blood pressure*	X	X			X	X (6)	X		X
12-lead ECG** (7)	X	X			X	X (7)	X		X
Ophthalmological examination* (8)	X	X			X				X
OCT* (8)	X	X							X
Spirometry*	X	X			X				X
Hematology/chemistry**	X	X			X				X
Urinalysis*	X	X			X				X
Lymphocytes**	X	X			X				X
Lymphocyte subsets** (9)	X	X		X	X				
JCV serology**	X	X							

Pregnancy test*/** (10)	X	X		X				X

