5.3.1.1 Study treatment exposure

Study treatment start date is defined as the earliest study drug start date documented in the study drug administration or study drug log eCRF pages, as listed above.

The time of study treatment start (time of first exposure to treatment) is taken from the study drug administration eCRF, where the date is equal to the study treatment start date, if available.

The EOT date is defined as the latest study treatment end date, as recorded on the Study Drug Log eCRFs listed above.

The following exposure variables are derived:

Duration of Study Treatment (days) = EOT date - Study treatment start date + 1 day. Duration of Study Treatment is also derived in weeks (days divided by 7), months (days divided by 30.4375), and years (days divided by 365.25).

Duration of Study Treatment is categorized as follows: ≤ 24 weeks (168 days), > 24 weeks to ≤ 48 weeks (336 days), > 48 weeks to ≤ 72 weeks (504 days), > 72 weeks to ≤ 96 weeks (672 days), > 96 weeks to ≤ 120 weeks (840 days), > 120 weeks to ≤ 144 weeks (1008 days), > 144 weeks (1008 days).

‘Study treatment exposure, interruptions excluded’ equals the ‘Number of days with intake documented’ for a subject overall as defined as part of the compliance derivations described in Section 5.3.1.2.1.

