5.6.2 Lymphocyte subsets

A sub-study assessing lymphocyte subsets will be conducted in approximately 200 subjects. Participation in the sub-study will be mandatory for all subjects until at least the first 200 subjects are randomized to the main study. T cell, B cell, and NK cell counts as well as T cell subsets (e.g., CD4⁺ naïve, CD4⁺ effector memory, CD4⁺ central memory, CD8⁺ naïve, CD8⁺ effector memory, CD8⁺ central memory, CD8⁺ terminally differentiated effector memory, Th17 cells, Treg cells, and Th1 cells) will be analyzed at the central laboratory. All subjects were to be analyzed for T cell subsets. In addition, the approximately 50 subjects were to be analyzed for B cell subsets. Other lymphocyte subsets may also be analyzed. Selected lymphocyte subsets may also be analyzed functionally *ex vivo*.

Blood samples for lymphocyte subset analysis will be taken from approximately 200 subjects at Visit 2 (Baseline), Visit 6 (Week 12), Visit 7 (Week 24), Visit 9 (Week 48), Visit 13 (Week 96), Visit 17 (Week 144), Visit 18 (EOT), Visit 19 (FU7d), and at Visit 20 (FU). If applicable, lymphocyte subsets will also be assessed at the corresponding visits in the PTOP (Visits 6A, 7A, 9A, 13A, 17A, and 18A).

Absolute and change from baseline values for lymphocyte subsets are derived as described in Section 5.5.12.

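### The derived Day-7 follow-up window opens at EOT + 6, one day after the FU7d visit is first permitted, so a compliant lymphocyte-subset sample at exactly EOT + 5 gets no Day-7 value.

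*SAP*

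**What the plan says.** Three parts of the SAP bear on this.

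- **Schedule.** Table 3 (Section 2.2) places FU7d at "Last study treatment intake + 7 days". The visit-window row gives it a tolerance of 2 days either side. Section 5.6.2 lists this visit among the sampling times for lymphocyte subsets.
- **Anchor.** Section 5.3.1.1 states: "The EOT date is defined as the latest study treatment end date, as recorded on the Study Drug Log eCRFs listed above". Sections 5.2.3.2 and 5.2.3.3 gloss EOT as last drug intake, so the schedule and the analysis window count from the same day.
- **Analysis window.** Section 11.4 summarizes most visits under their nominal label but makes exceptions, among them "Visit 19 (FU7d, Day 7 follow-up assessment for lymphocyte subset only), and Visit 20 (FU, Day 30 follow-up assessment). Those are derived following the rules" that follow. The Day-7 rule reads "Any assessment within EOT date + 6 days and EOT date + 15 days". The visit label enters only as a tie-break: "If multiple assessments fall into that period, the one corresponding to the regular FU7d visit (Visit 19) is selected".

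The neighbouring derived time points in Section 11.4 are last on-treatment, "the latest assessment prior to or on EOT date + 1 day", and Day-30 follow-up, "Any assessment within EOT date + 16 days and EOT date + 37 days".

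**The concern.** A derived analysis window should contain every day on which the visit it represents may properly take place. This one does not. A site that sees the subject on the first permitted day has followed the schedule, yet the rule leaves that subject without a Day-7 value. If the subject also has another assessment later in the window, that one is tabulated as Day-7 instead. Because the rule runs to EOT + 15, it would accept a sample taken well after the last permitted FU7d day while refusing a compliant one at EOT + 5.

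FU7d exists only for the lymphocyte-subset sub-study. It supplies the one derived time point between last on-treatment and Day-30 for those data. What is at stake is the completeness of that column.

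**Working it through.** No sample-size or test formula applies. The check compares ranges of days counted from EOT.

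**Inputs**

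- FU7d target and tolerance: +7, 2 days either way (Table 3).
- Derived Day-7 window: +6 to +15 (Section 11.4), read as including both ends. Reading the limits as exclusive would only widen the gap.
- Last on-treatment: up to +1 (Sections 5.5.1 and 11.4).
- Derived Day-30 window: +16 to +37 (Sections 5.5.1 and 11.4).
- FU visit: target +30, tolerance 7 days later only (Table 3).

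Table 3 was read from a PDF, so the alignment of its columns needs checking. The visit-window row has eight entries (±7, +7, ±2, +7, not applicable, ±1, +7, not applicable) for eight visit columns. The third entry belongs to FU7d.

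**Step 1: permitted FU7d days.** 7 − 2 = 5 and 7 + 2 = 9, so the days are {5, 6, 7, 8, 9}.

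**Step 2: permitted days outside the derived window.** {5, 6, 7, 8, 9} minus {6, …, 15} = {5}.

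**Step 3: does another derived time point catch day 5?** Last on-treatment stops at +1 and Day-30 starts at +16. Day 5 is in neither. The Visit 19 label does not help, because it chooses only among assessments already inside the window. The Section 11.3 remapping concerns premature EOT visits.

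**Step 4: comparison with the companion rule.** Permitted FU days are 30 to 37 and the derived Day-30 window is 16 to 37. No permitted day is left out, so only the Day-7 rule fails to contain its own visit.

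**Step 5: how many samples.** The SAP gives no distribution of FU7d visit days. If no visit falls on day 5, none is affected. If visits were spread evenly over the five days, 1/5 = 20% would be. Clustering near the day-7 target would give fewer than that. The even spread is an assumption made here for illustration and is not a figure from the SAP.

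**Step 6: shift in mean sampling day under that same assumption.** With all five days: (5 + 6 + 7 + 8 + 9)/5 = 35/5 = 7.0. Without day 5: (6 + 7 + 8 + 9)/4 = 30/4 = 7.5. The shift is half a day.

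**Step 7: after the change.** {5, …, 9} minus {5, …, 15} is empty. The window 5 to 15 still overlaps neither last on-treatment (up to +1) nor Day-30 (from +16).

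**The case against.** The case for leaving the text alone is that analysis windows often differ from operational visit windows. This one already runs six days past the last permitted visit day (15 − 9 = 6), so it was evidently not built to mirror the schedule. The summary in Section 9.10.2 is purely descriptive, with no hypothesis or model, in a synoptic report of a study stopped at 136 randomized subjects.

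This is fair on importance, but it does not explain the lower limit. A window wider than the schedule loses nothing, whereas one that starts later than the schedule leaves out compliant data, and the SAP gives no reason for starting at +6.

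The objection also disposes of several stronger readings that a reader might infer:

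- **That valid samples are discarded.** Section 11.4 only decides which value fills a derived column. The T-cell and B-cell analysis sets (Sections 7.1.4.2 and 7.1.4.3) require a baseline and an on-treatment sample, so no subject drops out for lacking a Day-7 value.
- **That a fifth of the data is lost.** This needs the even spread of Step 5, which the SAP does not support. Nor are all 136 subjects the denominator: being in the sub-study is not the same as having an FU7d sample, and B-cell subsets were planned in only about 50.
- **That Day-7 is the only early off-drug information.** The EOT visit also takes a subset sample and may occur up to 7 days late, so some EOT samples are off-drug too.
- **That a day-5 sample can never be tabulated anywhere.** Section 11.3 allows a visit to carry a second, scheduled-visit label, which could place a few such samples under a Week column. That would not supply the missing Day-7 value.

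**Conclusion.** The mismatch is real and confined to one day. A compliant Visit 19 sample at exactly EOT + 5 has no place in the derived Day-7 follow-up and falls in no other derived window. This rests on the column alignment of Table 3 and on EOT and last intake being the same date, both of which the SAP supports.

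The number of subjects affected is unknown and may be zero. It would be 20% under an even spread over the permitted days, and less if visits cluster near day 7.

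A reader might go further and infer that the summary is biased towards later lymphocyte recovery. The documents do not support that. Even under the even spread the mean sampling day moves only from 7.0 to 7.5, the same rule applies to both arms, and the SAP gives no recovery rate with which to turn half a day into a change in counts.

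The consequence is limited to a descriptive pharmacodynamic table. The primary, secondary and main safety analyses are untouched. It is a minor point, worth correcting because the rule as written omits on-schedule data.

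**What to change.** In Section 11.4, change the lower limit of the Day-7 follow-up window from EOT + 6 to EOT + 5. The window then contains every permitted FU7d day and stays clear of its neighbours.

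The alternative is to state that the nominal Visit 19 sample is always selected first, with the day window used only when there is none. If that route is taken, say whether a Visit 19 sample later than EOT + 15 still counts as Day-7.

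The first option is a one-digit edit plus the matching line in the derivation program. It changes no visit, no data collection and no other analysis. Its one side effect is that a sample at EOT + 5 from another visit, such as a late EOT visit, becomes eligible too. That is already so at EOT + 6 and + 7, and the existing preference for Visit 19 deals with it whenever a Visit 19 sample lies in the window.

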Subjects who prematurely discontinue study drug and complete the 30-day safety follow-up including the FU visit, will enter the PTOP which lasts until 60 weeks after randomization of the last subject or until Week 156, whichever is first (i.e., planned EOT visit) irrespective of treatment completion. The PTOP consists of an abbreviated schedule of assessments at the time of the originally scheduled 12-weekly visits (i.e., not all assessments are performed, see visit schedule). Safety follow-up visits are conducted in addition, following the post-treatment safety follow-up period schedule.

- **End-of-study:** the study level EOS occurs after all subjects have completed the safety follow-up period or the last visit of the PTOp. For an individual subject, EOS is reached when treatment, post-treatment safety follow-up, and if applicable, the PTOps have been completed:
 - For subjects who complete the treatment period, and for subjects who prematurely discontinue study treatment and do not enter the PTOp, the EOS visit corresponds to the 30-day follow-up visit (FU visit).
 - For subjects who prematurely discontinue study treatment and enter the PTOp period, the EOS visit corresponds to the last visit of the PTOp.

Table 1 **Dosing scheme**

Treatment period	Duration	Dose regimen in the ponesimod group
Titration	Day 1 and 2	2 mg
Titration	Day 3 and 4	3 mg
Titration	Day 5 and 6	4 mg
Titration	Day 7	5 mg
Titration	Day 8	6 mg
Titration	Day 9	7 mg
Titration	Day 10	8 mg
Titration	Day 11	9 mg
Titration	Day 12 to 14*	10 mg
Maintenance	Day 15 until EOT	20 mg

- * Visit 4 is to take place at Day 15 ± 1 day.
- EOT = End-of-Treatment.

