A safety assessment (ECG, vital signs, laboratory) is considered treatment-emergent, if the assessment date is on or after the study treatment start date and prior to or on the study treatment end date + 15 days (inclusive). If both, the assessment date/time and the date/time of study treatment start are available, only events with date/time on or after the date/time of study treatment start are considered to be treatment-emergent. In case of (partially) missing assessment dates/times, or for assessments on treatment Day 1 with reported assessment time contradicting the timepoint label, the nominal visit and timepoint labels will be used to determine whether an assessment is considered as treatment-emergent or not. For example, a blood pressure measurement with an assessment date on Day 1 but a missing assessment time or an assessment time after the time of first study drug intake, will not be considered treatment-emergent if reported under the timepoint “Pre-dose” in the eCRF, however it will be considered if reported as “2 hours post-dose” in the eCRF.

A safety event (AE, serious AE [SAE], Death) is considered treatment-emergent if the onset date/date of occurrence is on or after the study treatment start date and prior to or on the EOT date + 15 days (inclusive). Missing or partially missing onset or occurrence dates are imputed as described in Section 12.3. If both the onset/occurrence date/time and the date/time of study treatment start are available, only events with date/time on or after the date/time of study treatment start are considered to be treatment-emergent.

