9.9.5 Laboratory tests

Descriptive summary statistics by visit and treatment group are provided for laboratory test results reported by the central laboratory and corresponding absolute changes from baseline, based on the SAF. Except for 'Baseline', 'Last on treatment' and 'Day-30 follow-up', only treatment-emergent results from nominal scheduled visits are included; premature EOT visit is mapped to a scheduled visit [see Section 11.3]. Data are displayed in SI units as provided by the central laboratory. Values from unscheduled visits are not included in by visit summaries but are included in the listings and in the summaries for marked abnormalities and liver function test abnormalities.

For lymphocyte counts, this table is also provided on percent changes from baseline. The number of subjects with at least one treatment-emergent marked laboratory abnormality is summarized by treatment group, based on the SAF. The worst case in each direction is considered and summarized in all applicable categories, i.e., a subject counted in LLL is also counted in LL for a given parameter; also, a subject maybe counted in both the high and the low category for a given parameter. In addition, the number of subjects with treatment-emergent liver function test abnormalities is summarized by treatment group. The denominator for percentages is the number of subjects with at least one post-baseline assessment.

Safety laboratory hematology, clinical chemistry, urinalysis parameters planned as per protocol are also presented in subject data listings based on the SCR. All abnormalities and marked abnormalities including those at baseline are flagged in the listings.

A shift table of the frequency counts and percentages of number of subjects with positive, negative and indeterminate results at baseline and at EOS for JCV serology will be presented separately.

Other laboratory parameters are presented in a separate listing on the SCR.

Further analyses related to lymphocytes and lymphocyte subsets are described in Section 9.10.

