9.10.2 Lymphocyte subsets

All collected parameters from the T cell lymphocyte subset will be presented descriptively, with absolute values, as well as absolute and percent change from baseline values presented, using the T cell lymphocyte subset analysis set.

All collected parameters from the B cell lymphocyte subset will be summarized in the same way, using the B cell lymphocyte subset analysis set.

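### SAP 11.4 puts post-treatment observation period results into the nominal-week rows for safety and PD, against 9.9.3 to 9.9.6; for lymphocyte subsets nothing clearly overrides it

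*SAP*

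**What the plan says.** Section 11.4 of the SAP opens with a rule for both kinds of data: "Visit based safety and PD assessments are generally summarized according to the nominal visit". It then defines the rows as the derived baseline, "further scheduled nominal visits up to Week 156 (irrespectively if conducted during PTOp or not"), Last on-treatment, and the derived follow-up visits. One of those follow-up rows, Day-7, is reserved for lymphocyte subsets, so the layout is plainly meant to cover the subset tables.

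Section 9.9.5 (laboratory) says that, apart from Baseline, Last on treatment and Day-30 follow-up, "only treatment-emergent results from nominal scheduled visits are included". Sections 9.9.3 (ECG), 9.9.4 (vital signs) and 9.9.6 (spirometry) carry the same restriction. Section 5.5.1 ends the treatment-emergent window for an assessment "prior to or on the study treatment end date + 15 days (inclusive"). Section 9.10.1 sends the descriptive total lymphocyte tables to 9.9.5.

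For subsets, Section 9.10.2 says only: "All collected parameters from the T cell lymphocyte subset will be presented descriptively", with B-cell subsets handled in the same way. Section 5.6.2 says that, if applicable, "lymphocyte subsets will also be assessed at the corresponding visits in the PTOP", and names Visits 6A, 7A, 9A, 13A, 17A and 18A. On entry to the PTOP, Section 2.1.1 says that subjects who stop study drug early and "complete the 30-day safety follow-up including the FU visit, will enter the PTOP".

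**The concern.** Including PTOP visits at their nominal week suits an efficacy analysis that follows everyone regardless of treatment. It does not suit a pharmacodynamic table, which should describe lymphocyte subsets while subjects take ponesimod with DMF. A PTOP sample comes from a subject who stopped study drug at least a month earlier. If it sits in the ponesimod column at the same nominal week as on-drug samples, the row mixes two states. Where the effect reverses after stopping, the row understates it. The understatement grows if the off-drug share rises at later weeks, and a stable effect could then look as if it wanes.

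For the safety tables the issue is one of instruction. Two sections give a programmer different rules for which records enter a row, and the SAP does not say which comes first.

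**Working it through.** **1. Can a PTOP sample be treatment-emergent?**
- Treatment-emergent limit (5.5.1): EOT + 15 days.
- PTOP entry (2.1.1): after the safety follow-up visit, planned about 30 days after the last dose.
- Gap: 30 − 15 = 15 days.

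As planned, every PTOP sample falls at least about 15 days outside the window. Every PTOP result that 11.4 admits, 9.9.3 to 9.9.6 exclude.

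**2. Which rule reaches which table?**

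| Table | Restriction in its own section | Result |
|---|---|---|
| ECG, vital signs, laboratory, spirometry | Yes (9.9.3 to 9.9.6) | Conflicts with 11.4; the specific text probably prevails |
| Total lymphocytes by visit | Yes, through 9.10.1 to 9.9.5 | Same |
| T- and B-cell subsets | None in 9.10.2 | 11.4 is the only explicit rule |

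**3. Do the subset analysis sets remove the off-drug samples?** No. Sections 7.1.4.2 and 7.1.4.3 require at least one evaluable baseline and one evaluable on-treatment sample per subject. They select subjects, not samples. A qualifying subject's later PTOP samples stay in.

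**4. How large could the effect be?** The SAP gives neither the number of subjects in the PTOP nor a rate of recovery, so both are assumed. Let D be the on-drug ponesimod-placebo difference, f the share of ponesimod samples in a row that come from the PTOP, and r the fraction of the effect lost off drug. Assume that the placebo column is unchanged and that no other therapy acts on the counts. Then

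displayed difference = (1 − f) × D + f × (1 − r) × D = (1 − f × r) × D.

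| f | r = 0.5 | r = 1 |
|---|---|---|
| 10% | 1 − 0.05 = 95% | 1 − 0.10 = 90% |
| 20% | 1 − 0.10 = 90% | 1 − 0.20 = 80% |
| 30% | 1 − 0.15 = 85% | 1 − 0.30 = 70% |

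The retained effect runs from 70% to 95% over this range. With on-drug samples only, f = 0 and it is 100%.

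**5. Where could f be largest?** Possibly in the Week 156 row. Section 2 required PTOP subjects to have Visit 18A within 4 weeks of the termination decision, and Table 4 labels that visit W156A. Section 11.3 remaps by day only premature EOT visits, so nothing moves 18A to the subject's actual week. Enrolment began in March 2017. If the first randomization was on 1 March (assumed), the treatment day was 1001 on 26 November 2019 and 1057 after the 8 weeks allowed for the EOT visit. If it was on 31 March, the second figure is 1027. The Week 156 window in Table 6 opens at Day 1051, so few on-drug samples, if any, could reach that row.

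**The case against.** The strongest reply has four parts.

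*General versus specific.* Section 11.4 speaks of what is generally done and mainly fixes row labels and visit mapping. Sections 9.9.3 to 9.9.6 state four times which records enter. A programmer building those tables has a direct instruction. This largely stands. A reader might infer that the safety and total lymphocyte tables will be filled with off-drug data; the documents do not support that. What remains is that no order of precedence is written down.

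*Subsets may fall under 9.9.5.* They are analysed at the central laboratory, 5.6.2 derives them as in 5.5.12, and 9.9.5 refers to 9.10 for further analyses of subsets, which could mean analyses in addition to its own. The reading is possible but not clear. The parameter list in 5.5.12 omits subsets, and 9.10.2 neither repeats the restriction nor points back to it.

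*Not every early stopper contributes.* A reader might infer that a subject who stopped at Week 8 automatically adds off-drug Week 24 and Week 48 values. Scheduled on-treatment subset samples start at Week 12, so that subject needs an evaluable on-treatment sample from the premature EOT visit to be in the analysis set at all. That visit may fall up to 7 days after the last dose, while 5.5.1 counts an assessment as last on-treatment only up to EOT + 1 day. The example is conditional.

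*Size, direction and weight.* Section 7.1.2 foresees switches to other MS treatments, which could move counts either way. The tables are descriptive, the report is synoptic with 136 subjects randomized, and the Last on-treatment, Day-7 and Day-30 rows stay separate. All of this stands. It limits the consequence but does not justify the mixed rows.

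**Conclusion.** The point holds as a drafting conflict with one practical consequence. Section 11.4 and Sections 9.9.3 to 9.9.6 cannot both apply to the same table. Where 9.9 speaks, it probably prevails. For T- and B-cell subsets, 11.4 as written lets PTOP samples enter the on-drug rows, and no section clearly prevents it.

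The result can be a distorted description of the on-drug subset effect, most likely toward placebo. That direction needs three things: PTOP subset samples exist, the effect at least partly reverses off drug, and no switch of therapy offsets the reversal. A reader might infer that dilution is established, or that it is of a known size. It is not: the 70% to 95% retained effect rests on assumed shares and reversal, and the Week 156 remark rests on an assumed first randomization date. No test, p-value or error rate is affected.

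**What to change.** In 11.4, delete the PTOP clause for the safety and PD by-visit tables. The efficacy paragraph later in that section has its own PTOP clause and loses nothing. In 9.10.2, add the restriction already used in 9.9.5: apart from Baseline, Last on treatment, Day-7 follow-up and Day-30 follow-up, nominal-week rows take treatment-emergent results from scheduled visits only. List the PTOP subset samples, Visit 18A included, or show them in separate rows.

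The cost is two small text changes and a record filter that the laboratory tables already need. The downside is slightly fewer records at late visits. The filter still admits samples up to 15 days after the last dose, in line with the SAP's handling of its other by-visit safety tables.
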